#### - Consultant breast surgeon

- Patient's age subdivided in to
  - < 50
  - $\geq$  50 years of age
- Breast density\*
  - a) BIRADS Group 1 (pattern 1 only)
  - b) BIRADS Group 2 (pattern 2, 3 and 4).

\*Homogeneously or heterogeneously structured dense fibroglandular tissue in a large percentage of the entire breast volume is the only mammographic or ultrasound finding to date which has helped define a subgroup of patients with multi-focal or multi-centric disease detected by MR imaging alone (Fischer et al, 1999; Berg and Gilbreath, 2000). Mammograms will be evaluated according to the Breast Imaging Reporting and Data System (BIRADS) and patients divided in to two groups – Group 1 in which the breast is almost entirely fatty (pattern 1) and Group 2 encompassing those with scattered fibro-glandular densities that could obscure a lesion on mammography (pattern 2); those in whom the breast tissue is of heterogeneous density (pattern 3); and those with extremely dense breast tissue (pattern 4).

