# 8. DATA COLLECTION

Data generated by all centres will be collected, monitored and computerised by the NYCTRU. All centres will be asked to complete a log of all patients who are approached to enter the trial including those who refuse randomisation. Data collection for randomised patients will include: initial clinical details pre-randomisation, surgical procedure performed, histopathology, postoperative information, hospital re-admission, and recurrence details as listed below. As some variations in ancillary management (e.g. radiotherapy) and pathological examination exist between centres, the current management policies of each centre will be recorded at baseline and adherence to these policies monitored.

Attempts have been made to reduce data collection to a minimum, with the majority of data being completed by the research nurse and much of the remainder being collected routinely within the framework of the NHS BSP.

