### **10. STATISTICAL CONSIDERATIONS**

#### **10.1** SAMPLE SIZE

Assuming that the addition of MR imaging will reduce overall repeat operation or mastectomy rates following inadequate wide local excision from approximately 15% to 10%, a total of 1840 patients is required, using a chi-squared test without continuity correction, to detect benefit with 90% power at the 5% (2-sided) significance level (Machin et al, 1997).

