#### **10.2** ACCRUAL

Accrual at centres will be restricted by scanner, research nurse and radiologist availability. It is anticipated that consent rate of 50% of patient approached will be achievable. We therefore propose to recruit up to 50 centres over the course of the trial that will each recruit approximately 1 patient per week. Randomisation will be equally split to MR imaging or no MR imaging. As the project is funded by the NHS HTA programme, we anticipate that NCRN research will assist in the recruitment process.

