#### **11.1 PRIMARY ENDPOINTS**

#### 11.1.1 REPEAT OPERATION OR MASTECTOMY RATE

- i) The chi-squared test without continuity correction will be used to compare the proportion of patients in the two trial arms who have a repeat operation or mastectomy. 95% confidence intervals will be reported.
- ii) A logistic regression model will be fitted, adjusting for the stratification variables and other covariates that are identified as being prognostic of outcome. The adjusted analysis will be reported with the unadjusted analysis.
- iii) The impact on the primary endpoint of those patients who choose mastectomy, rather than WLE outside of the definitions for mastectomy within the trial, will be investigated in a sensitivity analysis. In this analysis we will assume that such patients would either all have undergone repeat operation or mastectomy (following initial surgery) or had no further surgery, and investigate how this affects the conclusions in the primary analysis.
- iv) Multi-level modelling will be performed to explore whether there is a surgeon effect, and within the MRI arm whether there is a radiologist effect.

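### The radiologist effect is explored in the MRI arm only, with no stated centre term and no use of control patients, so differences between centres in re-operation can be read as differences between radiologists.

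*Combined protocol and SAP*

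**What the plan says.** Section 11.1.1 item iv) plans multi-level modelling to "explore whether there is a surgeon effect, and within the MRI arm whether there is a radiologist effect". It does not say whether surgeon and radiologist enter one model or two, names no centre term, and gives control patients no part in the radiologist question.

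Other sections bear on this:

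- Section 8 expects sites to differ: "some variations in ancillary management (e.g. radiotherapy) and pathological examination exist between centres".
- Section 10.2 proposes to "recruit up to 50 centres over the course of the trial" and lists radiologist availability among the limits on accrual at a centre.
- Section 6.2 has "Consultant breast surgeon" as a minimisation factor, so each surgeon's patients should be roughly balanced between the arms.
- Section 8.1 records hospital and surgeon for every randomised patient. Section 8.3 records the radiologist with the MR findings.
- Section 5.2.1 has the images evaluated by a consultant radiologist. No section gives the number of MR radiologists per centre or says how scans are shared among them.
- Section 11 confines formal testing to the primary endpoints.

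**The concern.** A radiologist's MRI-arm re-operation rate has two parts: what the reading contributed, and how often patients at that hospital are re-operated on anyway. The second part depends on the surgeons and on how margins are examined and reported, and the protocol expects both to vary. If a reader works at one centre and only scanned patients are analysed, the local baseline goes into the reader's estimate.

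The control patients of the same surgeons and centres show that baseline directly, and minimisation on surgeon makes them a fair comparison. Item iv) does not say that they will be used.

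The stake is interpretation. The trial is pragmatic and meant to inform NHS provision, so readers will ask whether MR performs similarly across hospitals and operators. The analysis as written can suggest reader differences where there are none. It can also mask a real one where a good reader works with surgeons who re-operate often.

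**Working it through.** **The plan's own figure.** Section 10.1 states that "a total of 1840 patients is required, using a chi-squared test without continuity correction". The inputs there are rates of 15% and 10%, a two-sided 5% level and 90% power. With pooled variance under the null (mean rate 0.125):

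n per arm = [1.960 × √(2 × 0.125 × 0.875) + 1.282 × √(0.15 × 0.85 + 0.10 × 0.90)]² / 0.05² = (0.9167 + 0.5977)² / 0.0025 ≈ 917.3, so 918 per arm and 1836 in total.

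This agrees with 1840; power at 920 per arm is 90.1%.

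**Information available to item iv).** With 50 centres the MRI arm has 920 / 50 = 18.4 patients per centre. At 10% it has 92 events, or 92 / 50 = 1.84 per centre.

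**Why one reader per centre matters.** Let c be the centre effect (SD σc) and v the radiologist effect (SD σv), both on the logit scale.

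- MRI arm only: logit p = β + c + v. With one reader per centre only the sum c + v is seen, so the fitted SD targets √(σc² + σv²). With σv = 0 it estimates σc and labels it radiologist.
- Both arms: control logit p = α + c; MRI logit p = α + δ + c + v. The control patients estimate c, so v can be separated from it.

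**Simulation.** There were 50 centres, 18 patients per arm per centre, rates of 15% and 10%, one reader per centre and 120 runs per setting. The test was a boundary likelihood-ratio test at nominal 5% (cut-off 2.706). The centre SDs are assumptions, because the documents give none. For scale, around a 10% rate, centres one SD below and above would have rates of 7.6% and 13.0% (SD 0.3), 6.3% and 15.5% (SD 0.5), or 5.2% and 18.3% (SD 0.7).

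| σc | σv | MRI arm only: declared | median fitted SD | both arms: declared | median fitted SD |
|---|---|---|---|---|---|
| 0 | 0 | 6% | 0.00 | 4% | 0.00 |
| 0.3 | 0 | 9% | 0.25 | 0% | 0.00 |
| 0.5 | 0 | 47% | 0.47 | 0% | 0.00 |
| 0.7 | 0 | 86% | 0.66 | 0% | 0.00 |
| 0.5 | 0.5 | 85% | 0.65 | 32% | 0.44 |

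Neither model here has a surgeon term. The simulation error is √(0.47 × 0.53 / 120) ≈ 4.6 percentage points at 47% and √(0.09 × 0.91 / 120) ≈ 2.6 points at 9%. A separate set of 200 trials at σc = 0.5 gave 48% for the MRI arm only and 3% for a both-arm model with a random MR effect. In the last row the MRI-arm model's 85% is not useful power: 47% is declared with no radiologist effect at all.

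**Adding a surgeon term within the MRI arm, one reader per centre, no true radiologist effect.**

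- Purely surgeon-level variation (SD 0.5, assumed; 200 runs): with two surgeons per centre, false declarations fall from 15% to 3%; with three, from 13% to 2.5%.
- Centre SD 0.3 as well: they fall from 26% to 8.5%. Another set of 150 runs with a surgeon term gave 4% at centre SD 0.3.
- Larger centre variation, two surgeons per centre, surgeon term included (150 runs per setting): 21% to 29% at centre SD 0.5 and 63% at SD 0.7.

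**Two readers sharing two surgeons in each centre, MRI arm only (surgeon SD 0.5, 1500 runs).** With no true radiologist effect, a crude radiologist test rejects in 17.5%, 28.5% and 57.3% of runs at centre SD 0, 0.3 and 0.5. A surgeon-stratified test rejects in about 2%. Its power at centre SD 0.3 is 14% for a radiologist SD of 0.5 and 48% for 0.8.

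**The case against.** The strongest case on the other side has four parts.

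- **Structure is not stated.** The documents do not say that a centre has one reader. A reader might infer that radiologist and surgeon can never be separated inside the MRI arm. The documents do not support that: with several readers sharing surgeons, stratifying by surgeon separates them (about 2% false positives), though with low power.
- **A surgeon term fits the text.** Item iv) names surgeon and radiologist effects in one sentence, so a joint model is a fair reading. It largely removes purely surgeon-level confounding. It would therefore go too far to say that ordinary surgical variation will be taken for radiologist variation. Centre-level variation is not removed, and section 8 says that centres differ.
- **Size is assumed.** No between-centre SD is given, and at 0.3 the false-positive rate is only about 9%. The range, not any single value, is the result.
- **The analysis is exploratory.** Section 2 has no objective on variation between readers. Section 13.5 provides central review of scoring and section 11.2.5 compares MR with histopathology. This limits the importance of the point. Those checks, however, concern reading accuracy; they do not correct a model of re-operation.

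Restricting the radiologist effect to the MRI arm is itself natural, since only those patients are scanned. The gap is the missing baseline.

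**Conclusion.** The point holds in a limited form. As written, the radiologist analysis has no stated protection against centre-level differences in re-operation. With one reader per centre and no true effect, an MRI-arm-only model without a surgeon term declares one in about 9%, 47% or 86% of runs at an assumed centre SD of 0.3, 0.5 or 0.7. With a surgeon term the problem remains at the larger centre SDs (21% to 29% at 0.5, 63% at 0.7). It shrinks where centre variation is small or where several readers share surgeons. These figures rest on 50 equal centres and on assumed SDs and staffing.

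A reader might infer that the trial's main conclusion is at risk. It is not: the primary chi-squared test and the sample size do not depend on item iv). This is a cheap improvement to an exploratory analysis.

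**What to change.** Replace the radiologist part of item iv) with one exploratory multi-level logistic model fitted to both arms, containing:

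- a fixed MR effect;
- random intercepts for centre and for surgeon within centre;
- a radiologist random effect that acts only in MRI-arm patients, so that no radiologist need be assigned to control women.

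Report the radiologist SD with a 95% confidence interval, and the number of MR radiologists per centre. State that, where a centre has a single MR radiologist, this SD measures variation in the MR effect between centre pathways (reader, scanner and team together) and not the reader alone.

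The cost is a change of SAP wording and one different model. Hospital, surgeon and radiologist are already collected under sections 8.1 and 8.3. The downside is a wider interval and low power: in the simulation, which had no surgeon term, a radiologist SD of 0.5 at centre SD 0.5 was detected in about 32% of runs. The SD and its interval should therefore be reported as description, and a null result should not be read as showing that readers are alike.

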#### **11.1.2 HEALTH ECONOMICS ASSESSMENT**

The economic evaluation will take the form of a cost-effectiveness analysis and will consist of two parts. The first will be a within-trial comparison of the costs of the two forms of management related to differences in recurrence rates over a five-year period. The second part will involve the use of decision modelling and published data to extrapolate any differences in recurrence rates at five years to longer-term costs and quality-adjusted life expectancy.

#### WITHIN-TRIAL ANALYSIS

i) Estimating costs. Costs will be estimated from a societal perspective, that is, all costs will be considered no matter on whom they fall. In practice, this is likely to include health service costs (hospital and community-based) and patients' productivity costs. Detailed patient-specific resource use data will be collected after randomisation at the end of the first year of the study. From the health service perspective, these will include details of surgical procedures, key diagnostic procedures, hospitalisations, radiotherapy, chemotherapy, adjuvant therapy, use of primary care and other community-based resources. Details will also be collected of the duration of a woman's stay away from usual activities. Case record forms and questionnaires will be supplemented by detailed assessment of hospital notes in those patients who experience a recurrence over the period of the study. Resource use will be valued in monetary terms using a mixture of published UK unit costs (e.g. British

National Formulary for drug costs (British National Formulary, 2000)) and existing estimates of the unit costs of community-based resources (Netten et al, 1999). Unit costs for hospital resources (e.g. cost per night in a surgical ward, pathology costs, costs per minute in theatre) will be estimated, in collaboration with hospital finance staff, in a sample of trial centres. Productivity costs will be estimated in two alternative ways (Gold et al, 1996): (a) the standard human capital method based on the average UK wage and (b) with adjustment for the extent to which periods away from work are longer than the friction period (i.e. the 'friction cost' method).

Estimating effects. The key measure of effect for the within-trial cost-effectiveness analysis will be recurrence rates over five years. The within-trial analysis will, therefore, relate differential (societal) costs to differential recurrence rates. Within the trial, patients will also be asked to complete the EQ-5D instrument – a preference-based measure of health status - which will facilitate patient-specific health state values over time (Kind, 1996). Whilst the use of the EQ-5D will facilitate a valuable single-index measure of health within the trial, its main use for the economic evaluation will be to provide health state values (utilities) for the extrapolation modelling (see (i) below). The within-trial cost-effectiveness analysis will include discounting of costs and effects (Department of Health, 1995), adjustment for differential follow-up (Lin et al, 1997) and a stochastic analysis using cost-effectiveness acceptability curves (Van Hout et al, 1994).

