#### 5.2.2 MR IMAGING AT 12 MONTHS

All patients with lesions < 5mm in diameter or  $\geq$  5mm in diameter and biopsy negative, should undergo repeat DCE-MRI at 12 months post-radiotherapy, to assess persistence of change. Repeat core biopsy/ fine needle aspiration cytology should be carried out for indeterminate/ suspicious enhancing lesions that are  $\geq$  5mm in diameter.

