#### **11.2** SECONDARY ENDPOINTS

#### **11.2.1 RECURRENCE RATE**

The analysis of time to ipsilateral breast tumour recurrence will be conducted up to five years post completion of radiotherapy (i.e. when there is at least five years follow-up for all patients). Cox's Proportional Hazards Model will be fitted. Adjustment will be made for the stratification variables and other covariates that are identified as being prognostic of outcome. Treatment effects will be

expressed as hazard ratios. Point estimates will be reported with 95% confidence intervals without formal hypothesis testing, as it is anticipated that the trial will have insufficient power to detect differences between the trial arms in recurrence rates.

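### The within-trial economic analysis spans five years, but costs are scheduled for all women for only about one year, and nothing says the later MR-arm scans and biopsies are costed

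*Combined protocol and SAP*

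**What the plan says.** Section 9.1.2 makes the economic evaluation a primary endpoint and relates costs to ipsilateral recurrence out to 60 months. Section 11.1.2 describes the within-trial part as costs "related to differences in recurrence rates over a five-year period", and its extrapolation subsection says the trial is designed to estimate both cost and recurrence differences over five years.

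On data, the within-trial subsection says: "Detailed patient-specific resource use data will be collected after randomisation at the end of the first year of the study". It adds a "detailed assessment of hospital notes in those patients who experience a recurrence over the period of the study". Section 8.8 agrees with this. Re-admissions and further surgery are recorded at 6 months and treatments at 12 months, then only recurrences and status up to 5 years. Under section 7.2 the questionnaires, which carry the economic items and EQ-5D, end 12 months after initial surgery.

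Section 5.2.2 says that MR-arm women with lesions under 5 mm, or larger but biopsy-negative, "should undergo repeat DCE-MRI at 12 months post-radiotherapy, to assess persistence of change". Repeat sampling follows for some of them. Section 5.2.1 also sends women with two indeterminate samples to repeat imaging.

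On EQ-5D, the plan says "its main use for the economic evaluation will be to provide health state values (utilities) for the extrapolation modelling". On recurrence, section 11.2.1 says "it is anticipated that the trial will have insufficient power to detect differences between the trial arms in recurrence rates".

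**The concern.** A cost-effectiveness ratio needs costs and effects over the same period. Here the effect runs to 60 months. The costs run to about 12 months for everyone, and later only for women who have the outcome event, so the amount of cost data in years 2 to 5 depends on the outcome itself. The planned adjustment for unequal follow-up deals with women whose follow-up is cut short. It cannot supply costs that nobody was scheduled to record.

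The gap also falls unequally on the arms. The repeat scans and their biopsies are required by the protocol, occur only in the MR arm, and come after the cost window. If they go uncosted, the error is one-sided and makes MR imaging look cheaper than it was, although section 11.1.2 adopts a societal perspective that counts costs whoever bears them.

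**Working it through.** **1. The plan's own sample size.** Inputs from section 10.1: "from approximately 15% to 10%, a total of 1840 patients is required", "to detect benefit with 90% power at the 5% (2-sided) significance level", chi-squared test without continuity correction. Section 3 gives equal allocation.

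n per arm = [1.960·√(2p̄q̄) + 1.282·√(p₁q₁ + p₂q₂)]² / (p₁ − p₂)², with p̄ = 0.125

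= [1.960·√0.21875 + 1.282·√0.2175]² / 0.05² = 917.3, so 918 per arm and 1836 in total.

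This reproduces 1840, and power at 920 per arm is 90.1%. The trial is correctly sized for repeat operation or mastectomy. No design figure is given for recurrence or for the economic endpoint.

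**2. Cost window against effect window.**

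| Item | Section | Period |
|---|---|---|
| Effect (recurrence) | 9.1.2, 11.1.2 | to 60 months |
| Cost comparison as described | 11.1.2, extrapolation modelling | five years |
| Resource use, all women | 11.1.2, costs; 8.8 | to about 12 months |
| Patient questionnaires | 7.2 | to 12 months after initial surgery |
| Hospital-notes review | 11.1.2, costs | whole study, recurrence cases only |

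I read the first year of the study as each woman's first year. Share of the horizon costed for women who do not recur: 12/60 = 20%.

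The documents give no five-year recurrence rate for this population, so I assume 3% to 11%. The upper end is the figure in section 1 for uni-focal tumours without radiotherapy. Women with no scheduled cost data after month 12: 1840 × 0.97 = 1785 down to 1840 × 0.89 = 1638.

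**3. When the repeat scans fall.** Let initial surgery be s months after randomisation and radiotherapy m months after it, with m > s > 0. The scan is at m + 12. That is later than month 12, and later than the last questionnaire at s + 12, whatever the values of s and m.

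**4. Size of the possible understatement.** Missing cost per MR-arm woman = f × (scan cost + b × biopsy cost), where f is the share of the arm re-scanned and b the share of those re-sampled. The documents give neither f, b nor the unit costs. Each percentage point of f is 920 × 0.01 ≈ 9 scans. The direction is known and the amount is not.

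**5. Recurrence precision, for scale.** With 920 per arm and MR-arm rate = 1 − (1 − control rate)^HR, the power of the two-sided 5% chi-squared test is as follows (rates and hazard ratios are assumed):

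| Control rate | HR 0.50 | HR 0.67 | HR 0.75 |
|---|---|---|---|
| 3% | 58% | 27% | 17% |
| 5% | 80% | 41% | 25% |
| 8% | 94% | 60% | 37% |
| 11% | 99% | 73% | 48% |

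Example: at 5% and HR 0.67 the MR-arm rate is 1 − 0.95^0.67 = 3.4%. The difference is 1.6 points and the 95% half-width is 1.96·√(0.05·0.95/920 + 0.0338·0.9662/920) = 1.8 points. This agrees with section 11.2.1 except where the effect is large.

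**The case against.** The defence has four parts.

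- **The scans.** A reader might infer that all repeat scans are excluded from costing. No section says so. Diagnostic procedures are a listed cost item, section 8.3 records additional biopsies, section 13.5 sends a copy of each MR examination to the trials unit, and section 9.2.7 documents management changes prompted by the small lesions. The number of scans is unknown, and if they are judged research-only, leaving them out could be right. This stands against a claim of exclusion. It does not close the gap, because the listed items belong to first-year collection and nothing commits the plan to costing later scans.
- **Years 2 to 5.** Notes review covers women who recur, and their later costs are those most directly tied to the chosen effect. Routine follow-up of the others occurs in both arms and should largely cancel. This stands, and it makes the shared part of the gap less harmful than the counts suggest. It does not apply to the MR-only scans.
- **Power.** A reader might infer that the effect cannot be separated from zero and the ratio is therefore worthless. Section 11.2.1 only anticipates insufficient power, a large effect would be detectable, and the planned acceptability curves do not need a significant recurrence difference. Low power means an uncertain result, not an invalid one.
- **EQ-5D.** A reader might infer that it is left out of the within-trial result. The plan gives extrapolation as its main use, not its only one, and describes a within-trial health index. What is missing is a specified within-trial QALY analysis.

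Section 11 is also headed as an outline. That explains the brevity, but not the conflict over the costing period.

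**Conclusion.** The concern holds for the costing period and the MR-arm scans. Sections 9.1.2 and 11.1.2 describe a five-year comparison. The scheduled data support about one year of costs for all women, then recurrence cases only. If the schedule is followed and nothing is added, MR-arm cost is understated by the repeat scans and follow-on biopsies. The amount cannot be estimated from the documents.

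This rests on three readings: that the first year means each woman's first year, that radiotherapy follows surgery and randomisation, and that the absence of any costing statement for the scans means none is planned. The 89% to 97% share also depends on the assumed recurrence range.

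A reader might conclude that a 12-month cost-utility analysis should replace the five-year base case. The documents do not support that. It would set aside the defined 60-month endpoint, miss most of the recurrence period, and drop the very scans at issue, which fall after month 12. As an addition it is worthwhile. The data are already collected, and it could be reported at the first of the two analysis stages in section 11, whereas the five-year effect measure has to wait for the second.

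**What to change.** 1. Keep five-year cost per recurrence as the defined within-trial analysis. State that every repeat MR scan and follow-on biopsy is counted from the trial imaging records (sections 8.3 and 13.5) and costed. Add a sensitivity analysis without them in case they are judged research-only.
2. Reconcile the costs and extrapolation text of section 11.1.2 with section 8.8 on the costing period. State an explicit assumption for years 2 to 5 in women who do not recur, for example a standard annual follow-up cost applied equally to both arms.
3. Add, as a supplementary analysis, a 12-month cost-utility comparison. Use baseline-adjusted EQ-5D area under the curve by actual assessment dates, because the last questionnaire is timed from surgery and the costs from randomisation. Set it against first-year costs and report cost per repeat operation avoided alongside, all at the first analysis stage.

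The cost is protocol and analysis-plan wording plus some extra costing and analysis work, with no new patient assessments. MR imaging may look slightly more costly in the five-year result.
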